9.1.3 Adverse Event Procedures

All AEs are to be assessed in all subjects throughout the study period (from enrollment to study withdrawal or completion) and documented in the study eCRF. Each AE should be reported spontaneously or in response to general, non-directed discussion with the attending nurse or physician (eg, has there been any change in subject status since the last assessment period?). For each AE, the investigator should obtain all information required to complete the AE page of the eCRF, in accordance with eCRF completion guidelines (provided separately by Discovery).

All AEs, regardless of seriousness, severity, or relationship to study participation, must be recorded (using medical terminology) in the source document and on the AE page of the eCRF. Whenever possible, diagnoses should be given when signs and symptoms are due to a common etiology.

All AEs must be followed until resolution or until a stable clinical end-point is reached, or for at least 30 days after the subject's last day in the study if an AE is ongoing at the time the subject completes the study. All measures required for AE management and the ultimate outcome of the AE must be recorded in the source document and reported on the AE page of the eCRF.

9.1.4 Serious Adverse Events

A SAE is any untoward medical occurrence that, at any dose meets one of the following criteria (ICH E2A, *Clinical Safety Data Management: Definitions and Standards for Expedited Reporting*):

1. Results in death
2. Is life-threatening
3. Requires inpatient hospitalization or prolongation of existing hospitalization
4. Results in persistent or significant disability/incapacity
5. Is a congenital anomaly/birth defect
6. May be considered serious when based upon appropriate medical judgment

When the investigator-trained designee becomes aware of an SAE, Discovery must be notified as soon as possible (and no later than 24 hours after the event has occurred) by telephone, regardless of the relationship (or lack thereof) of the SAE to study participation.

SAEs should be reported to Discovery's reporting line (see Section 9.2).

When reporting SAEs, the following information should be provided:

- | | |
|-------------------------------|---|
| 1. Study identifier | 7. Clarification on whether study aerosol was discontinued |
| 2. Study center | 8. The reason why the event is classified as serious |
| 3. Subject number | 9. The Investigator's assessment of the association between the event and study participation |
| 4. A description of the event | |
| 5. Date of onset | |
| 6. Current status | |

All reports of SAEs must be followed up within 24 hours (or sooner at the request of the medical monitor) by the completion of the SAE form and signature by the person who completed the form and the PI. This should be emailed to the local clinical site monitor or faxed to Discovery at [contact] (USA).

In accordance with Discovery's standard operating procedures (SOPs) and regulatory agency (eg, FDA) regulations, investigators will be notified of the occurrence of serious, unexpected, related AEs. The PI must promptly inform the relevant IRB/IEC in accordance with ICH E6 of all AEs that are deemed related to study participation (ie, there is a reasonable possibility that the AE may have been caused by the drug or device) and are thus deemed a significant new AE or risks with respect to the drug or device.

9.1.5 Unanticipated Adverse Device Effects

An UADE is defined as any serious adverse effect on health or safety or any life-threatening problem or death caused by, or associated with, a device, if that effect, problem, or death was not previously identified in nature, severity, or degree of incidence in the investigator's brochure, or any other unanticipated serious problem associated with a device that relates to the rights, safety, or welfare of subjects.

In such cases, Discovery must be notified immediately through the following procedures:

- Contact the clinical site monitor or designated contact person regarding the event immediately.
- Complete all device reporting procedures detailed in the study manual.

10 DISCONTINUATION AND REPLACEMENT OF SUBJECTS

10.1 Early Discontinuation of Lucinactant for Inhalation

The PI or the subject's legal guardian may discontinue the administration of lucinactant for inhalation at any time point before or during the administration of lucinactant for inhalation. Discontinuation may be based on but not limited to the criteria outlined in Section 5.1.2.

1. Device failure or malfunction, including error codes or treatment interruptions
2. Pulmonary hemorrhage or other AE/ADE
3. In the PI's best medical judgment, initiating or continuing the subject's exposure to lucinactant for inhalation is not in the best interest of the subject's safety.
4. Signs of respiratory deterioration as evidenced by an increased respiratory rate or an observed increase in respiratory effort (work of breathing) plus at least one of the following: an $\text{FiO}_2 \geq 0.70$ or a sustained increase from baseline by ≥ 0.30 to maintain oxyhemoglobin saturation; a $\text{PCO}_2 > 70$ mm Hg or a progressive increase in PCO_2 from baseline to ≥ 20 mm Hg above baseline and confirmed with a blood gas; recurring episodes of bradycardia defined as a heart rate of < 100 bpm for ≥ 20 seconds; a sustained apneic event, defined as apnea at least 20 seconds in duration and meeting at least one of the following: (1) $\text{HR} < 100$ bpm, (2) desaturation (oxygen saturation $< 80\%$), (3) requirement for IPP breaths using inflating pressures above the set CPAP pressure administered manually or mechanically through any patient interface.

10.2 Study Withdrawal

A subject may withdraw consent (through their legally authorized guardian) at any time without prejudice to further care.

If, at the end of the Final Study Period, the status of a subject is unknown, every effort must be made to contact the subject's legally authorized guardian to determine the status of the subject. If the status of the subject has not been established in 28 days following exposure to study aerosol, the subject will be considered lost to follow-up.

10.3 Early Study Termination

The study may be terminated prematurely due to safety reasons by the SRC (Section 6).

Additional reasons for study termination include, but are not limited to, the following:

- The local or national regulatory agency requests a termination of the study.

- It has been determined that the risk level associated with the experimental drug is significant and warrants termination of the study.
- Discovery, for reasons other than safety, may terminate the study at any time by written notice of intended termination provided at least 30 days before termination.
- The PI or IRB/IEC, for reasons other than safety, may terminate participation of this clinical site in the study by written notice of intended termination provided at least 30 days before termination.
- Any other clause described in the individual site Clinical Study Agreement (eg, if ICH GCP guidelines or other regulatory procedures are not followed or if enrollment rate is not sufficient to meet study goals).

10.4 Replacement of Subjects

Subjects who discontinue treatment early or who are withdrawn from the study will not be replaced, unless required by the SRC in order to adequately assess safety in the dose group.

11 PROTOCOL VIOLATIONS

A protocol violation occurs when the subject or PI fails to adhere to any significant protocol requirement affecting the inclusion, exclusion, subject safety, and primary endpoint criteria. Protocol violations include but are not limited to the following:

- Failure to meet eligibility criteria
- Use of a prohibited concomitant medication (Section 7.3)
- Failure to comply with ICH GCP guidelines

Discovery will determine if a protocol violation will result in withdrawal of a subject.

When a protocol violation occurs, it will be discussed with the PI. All protocol violations will be documented and tracked.

12 ETHICS

This study will be conducted according to the United States and ICH regulations and guidelines (21 Code of Federal Regulations [CFR] Part 50, *Protection of Human Subjects*, 21 CFR Part 56, *Institutional Review Boards*, 21 CFR Part 312, *Investigational New Drug Application*, and ICH E6, *Guideline for Good Clinical Practice*) as well as all applicable local, state, and federal regulations and guidelines regarding the conduct of clinical studies. In addition, this study will be conducted in accordance with the ethical principles included in the World Medical Assembly (WMA) Declaration of Helsinki, *Ethical Principles for Medical Research Involving Human Subjects* adopted by the 18th WMA General Assembly, Helsinki, Finland, June 1964, and amended most recently by the 59th WMA General Assembly, Seoul, Korea, October 2008.

Throughout this section the term “Clinical Investigator” will be defined, in accordance with 21 CFR 54, as any listed or identified PI or subinvestigator who is directly involved in study dosing or evaluation of research subjects. PIs or subinvestigators must be listed on Form FDA 1572, if applicable, and also documented as appropriate on the delegation of authority signature log.

12.1 Institutional Review Board

The protocol, including any amendments and the ICF, will be submitted to an IRB at each investigational site for approval to conduct the study. Before the initiation of the study at each investigational site, a designee at the site will forward to Discovery a copy of the site’s local IRB approval to conduct study the study. This approval must refer to the study by exact protocol title and number and should identify the documents reviewed and the date of review.

Protocol and ICF modifications or changes may not be initiated without prior written IRB approval, except when necessary to eliminate immediate hazards to the study subjects or when the change(s) involves only logistical or administrative aspects of the study. Such modifications will be submitted to the IRB and written verification that the modification was submitted and subsequently approved should be obtained. A site must receive approval from Discovery on any ICF modification before submission to the IRB for approval and subsequent implementation at the study site. Protocol modifications (ie, amendments) may only be enacted by Discovery.

The IRB must be informed of revisions to other study-related documents or study information that was originally submitted for review. Revised study documentation and related informational updates may include but are not limited to the following:

1. Serious and/or unexpected AEs occurring during the study (reported in accordance with the SOPs and policies of the IRB)
2. Any new study information that may adversely affect subject safety or study conduct
3. Annual study updates or IRB requests for reassessment of the study
4. Timely communication of significant actions and related findings from the SRC (to include study enrollment holds or expansion, protocol amendments, or early study closure).
5. Notification of major study/site milestones to include study/site closure

12.2 Informed Consent Form of Study Subject

A signed ICF will be obtained in accordance with the Declaration of Helsinki, ICH GCP, 21 CFR 50 Subpart B, 2 and 21 CFR 56, Subpart A), HIPAA, and local regulations.

The PI will prepare the ICF and HIPAA authorization based on an ICF template provided by Discovery. Completed site-based ICFs must be provided to Discovery or designee for approval before submission to the IRB. The ICF generated by the PI must be acceptable to Discovery and be approved by the IRB. The PI will send an IRB-approved copy of the ICF to Discovery for the study file.

The subject's legally authorized guardian will be provided a consent form describing this study and be provided sufficient information to make an informed decision about the subject's participation in this study. The formal consent of a subject's legally authorized guardian, using the IRB-approved consent form (and any other locally required documents), must be obtained before the performance of any study-related activity, including the cessation of any medications or procedures. The consent form must be signed and dated including the time of consent by the subject's legally authorized guardian, the investigator-designated research professional obtaining the consent, and, if applicable, an impartial witness.

12.3 Financial Disclosure

The FDA has issued regulations (21 CFR Part 54, *Financial Disclosure by Clinical Investigators*) that require sponsors to submit complete and accurate certification or disclosure statements to certify the absence of certain financial interests of clinical investigators and/or to disclose those financial interests, as required, when clinical studies are submitted to FDA in support of marketing approval. These regulations are intended to ensure that financial interests

and arrangements of clinical investigators, that could affect reliability of data submitted to FDA in support of marketing approval, are identified and disclosed by the sponsor.

Clinical investigators will be asked to disclose proprietary (eg, patent, licensing agreement) and financial (eg, stock options, royalty) interests as they pertain to Discovery, before participating in the study. In addition, clinical investigators will be required to consult with Discovery before acquiring any financial interest in the company and must disclose any change in their proprietary or financial interests, if it occurs during the course of the study and for 1 year following study completion. The requirement for proprietary and financial disclosure also includes any ownership by the spouse or any dependent subject of the clinical investigator.

If FDA determines that the financial interests of any clinical investigator raise serious questions about the integrity of the data, FDA will take any action it deems necessary to ensure the reliability of the data, including:

1. Initiating agency audits of the data derived from the clinical investigator in question
2. Requesting that the sponsor submit further data analyses (eg, to evaluate the effect of the clinical investigator's data on overall study outcome)
3. Requesting that the applicant conduct additional independent studies to confirm the results of the questioned study
4. Refusing to treat the covered clinical study as providing data that can be the basis for an agency action

If the sponsor does not include certification or disclosure, or both (as required), or does not certify that it was not possible to obtain the information, the FDA may refuse to file the New Drug Application (NDA).

13 STATISTICAL METHODS AND DETERMINATION OF SAMPLE SIZE

It is anticipated that approximately 64 subjects will be enrolled into the study with approximately 32 subjects randomized to the active surfactant arm. The sample size is based on the number of subjects necessary to evaluate the safety and tolerance of lucinactant for inhalation.

Sample size calculations to demonstrate clinical effect will not be performed as efficacy is an exploratory objective.

A complete outline of the all planned analyses for the study, to include the handling of missing data, is provided in Statistical Analysis Plan.

13.1 Statistical and Analytical Plans

The statistical analysis will be based on all randomized subjects in the study, ie, the Intent-to-Treat (ITT) population. In addition, all evaluable subjects will be analyzed for efficacy signals. Evaluable subjects are those in whom complications of prematurity (eg, PDA, IVH, sepsis,) do not preclude assessment of efficacy signals (eg, improvement in oxygenation, need for intubation and IMV). For all variables, summary statistics will be provided by dosing group, including frequency count and percentage for discrete or categorical variables, and mean, standard deviation, median, minimum, and maximum for continuous variables. In addition, time-to-event variables will be summarized using Kaplan-Meier methodology. Incidence and rates of death, BPD, survival without BPD, and worst-stage ROP at 36 weeks PMA will be summarized.

If no values are recorded in a given eCRF data field, they will be treated as missing and will not be imputed.

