- In the PI's best medical judgment, initiating or continuing the subject's exposure to lucinactant for inhalation is not in the best interest of the subject's safety, such as hemodynamic instability.
- Signs of acute respiratory deterioration as evidenced by an increased respiratory rate or an observed increase in respiratory effort (work of breathing) plus at least one of the following:
 - a) An FiO₂ ≥ 0.70 or a sustained (≥ 10 minutes) increase from baseline by ≥ 0.30 to maintain adequate oxyhemoglobin saturation (SpO₂ $\geq 88\%$),
 - b) A PCO₂ > 70 mm Hg or a progressive increase from baseline to ≥ 20 mm Hg above baseline and confirmed with a blood gas,
 - c) Recurring episodes of bradycardia defined as a heart rate < 100 bpm for ≥ 20 seconds,
 - d) A sustained apneic event, defined as apnea for at least 20

seconds in duration and meeting at least one of the following: (1) HR < 100 bpm, (2) desaturation (oxygen saturation < 80%), (3) requirement for IPP breaths using inflating pressures above the set CPAP pressure administered manually or mechanically through any patient interface.

Enrollment hold criteria:

The study will be placed on enrollment hold until further evaluation by the SRC if one of the following criteria are met:

- If > 2 subjects per dosing group experience a SAE related to lucinactant for inhalation administration
- If ≥ 1 subject dies during first 12 hours following and related to lucinactant for inhalation administration

Statistical Analysis: The statistical analysis of both the primary and secondary safety and tolerability objectives will be based on all randomized preterm neonates in the study. In addition, data from all evaluable preterm neonates will be analyzed for efficacy signals as an exploratory endpoint. No hypothesis testing or statistical comparisons will be performed.

Interim Analyses: All available safety endpoint data captured from randomization to completion of 72 hours for active subjects, and all available safety endpoint data for control subjects, will be evaluated by the SRC. As this is an open-label study with no hypothesis testing, no adjustments for *p*-values are required or employed for the interim analyses.

TABLE OF CONTENTS

TITLE PAGE	1
AEROSURF PROTOCOL SUMMARY	3
TABLE OF CONTENTS	15
LIST OF ABBREVIATIONS	20
1 INTRODUCTION.....	22
1.1 Treatment of Neonatal Respiratory Distress Syndrome	22
1.1.1 Continuous Positive Airway Pressure in Neonatal Respiratory Distress Syndrome	23

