- AEs and ADEs (including peri-dosing events and nasal excoriations)
- Air leak (especially pneumothorax and pneumomediastinum)
- Survival
- Use of respiratory support and supplemental oxygen
- Complications of prematurity
- Assessments of the following:
 - a) Arterial carbon dioxide (PCO₂)
 - b) Serum electrolyte measurements
 - c) Vital signs
 - d) Gastric liquid volume
 - e) Oxygen saturations (SpO₂)
- Chest radiography prior to intubation, if such a procedure does not delay or compromise the emergent care of the subject

A peri-dosing event is defined as an adverse event with an onset time ≤ 2 hours from the time of initiating administration of lucinactant for inhalation

Efficacy endpoints (exploratory objective) in the study include:

- Incidence of bronchopulmonary dysplasia (BPD) at 36 weeks PMA
- Rate of survival without BPD at 36 weeks PMA
- Technical performance of the ADS
- Worsening respiratory status either during or after exposure to lucinactant for inhalation
- Physiological parameters (eg, FiO₂, PCO₂)

The statistical analysis of both the primary and secondary safety and tolerability objectives will be based on all randomized preterm neonates in the study. In addition, data from all evaluable preterm neonates will be analyzed for efficacy signals as an exploratory endpoint. As this is an open-label study with no hypothesis testing, no adjustments for *p*-values are required or employed.

TABLE OF CONTENTS

EXECUTIVE SUMMARY	3
1 OVERVIEW.....	9
1.1 BACKGROUND.....	9
1.1.1 Treatment of Neonatal Respiratory Distress Syndrome	9
1.1.2 Development of Aerosolized Device for Lucinactant Delivery	10
1.2 OBJECTIVES	11
1.2.1 Primary Objective	11
1.2.2 Secondary Objective	11
1.2.3 Safety Evaluations	11
1.2.4 Exploratory Efficacy Objective	12
1.3 HYPOTHESES.....	13
2 INVESTIGATIONAL PLAN	14
2.1 STUDY POPULATION	14
2.1.1 Inclusion criteria	14
2.1.2 Exclusion Criteria	14
2.2 STUDY DESIGN AND RANDOMIZATION.....	15
2.2.1 Treatment Groups	16
2.2.2 Repeat Dosing	16
2.2.3 Sample Size Justification	17
2.2.4 Study Schedule	18
3 STUDY SUBJECT CHARACTERISTICS.....	19
3.1 DEMOGRAPHICS AND BASELINE CHARACTERISTICS	19
3.1.1 Demographics	19
3.1.2 Birth and Maternal History	19
3.2 SUBJECT DISPOSITION	19
3.3 STUDY AND CONCOMITANT MEDICATION.....	20
3.3.1 Compliance	20
3.3.2 Number of Doses	20
3.3.3 Previous and Concomitant Medication	20

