4.1 EFFICACY POPULATIONS

The ITT population is the efficacy analysis population and is defined as all subjects who were randomized in the study.

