11 LIST OF TABLES

Table	Title
1.1	Subject Disposition – Study Populations – All Subjects
1.2	Subject Disposition – Study Completion/Termination Status – All Subjects
1.3	Subject Disposition – Protocol Deviations/Violations – All Subjects
2.1	Subject Demographics – Intent-to-Treat Population
2.2	Medical Information – Maternal History – Intent-to-Treat Population
2.3	Medical Information – Birth History – Intent-to-Treat Population
3.1	Concomitant Medications – Safety Population
3.2	Number of Treatments Received – Safety Population
4.1.1	Exploratory Efficacy Analysis – Early Worsening of Respiratory Status Criteria – Intent-to-Treat Population
4.1.2	Exploratory Efficacy Analysis – Late Worsening of Respiratory Status Criteria – Intent-to-Treat Population
4.2	Exploratory Efficacy Analysis – BPD and Survival Without BPD at 36 Weeks PMA – Intent-to-Treat Population
4.3	Exploratory Efficacy Analysis – Time until Intubation for Mechanical Ventilation – Intent-to-Treat Population
4.4	Exploratory Efficacy Analysis – Time until Any Intubation – Intent-to-Treat Population
5.1	Investigational Device – Technical Performance – Safety Population
5.2	Investigational Device – Early Termination of Treatment – Safety Population
6.1	Peri-Dosing Adverse Events – Safety Population
6.2	Air Leak – Safety Population
6.3.1	Treatment-Emergent Adverse Events by System Organ Class and Preferred Term – Safety Population
6.3.2	Treatment-Emergent Adverse Events by System Organ Class, Preferred Term, and Severity – Safety Population
6.3.3	Treatment-Emergent Adverse Events by System Organ Class, Preferred Term, and Relationship – Safety Population
6.3.4	Treatment-Emergent Adverse Events by Severity and Relationship to Study Drug – Safety Population
6.3.5	Treatment-Emergent Adverse Events in Descending Order by Total Active Group – Safety Population
6.4.1	Serious Adverse Events by Preferred Term Displayed in Descending Order by Total Active Group – Safety Population
6.5.1	Adverse Device Effects by Treatment Group – Safety Population
6.6	All-Cause Mortality – Safety Population

- 7.1.1 Clinical Assessments – Vital Signs – Body Temperature – Observed Values and Change from Baseline – Safety Population
- 7.1.2 Clinical Assessments – Vital Signs – Respiration Rate – Observed Values and Change from Baseline – Safety Population
- 7.1.3 Clinical Assessments – Vital Signs – Heart Rate – Observed Values and Change from Baseline – Safety Population

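### The protocol's evaluable efficacy set selects infants on outcomes that arise after randomization, while the SAP names ITT as the efficacy population and neither defines nor tabulates that set

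*Protocol*

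**What the plan says.** Protocol 13.1 starts from the full randomized set: "The statistical analysis will be based on all randomized subjects in the study, ie, the Intent-to-Treat (ITT) population". It then adds a second analysis: "In addition, all evaluable subjects will be analyzed for efficacy signals". Membership of that second set is defined by "Evaluable subjects are those in whom complications of prematurity (eg, PDA, IVH, sepsis,) do not preclude assessment of efficacy signals", and the section gives better oxygenation and need for intubation as examples of such signals.

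The protocol synopsis (Statistical Analysis) divides the work differently. The "safety and tolerability objectives will be based on all randomized preterm neonates in the study", and the next sentence reads "In addition, data from all evaluable preterm neonates will be analyzed for efficacy signals as an exploratory endpoint". The SAP executive summary repeats this pairing ("data from all evaluable preterm neonates will be analyzed for efficacy signals as an exploratory endpoint") without defining evaluable.

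The body of the SAP takes another position. Section 4.1 states: "The ITT population is the efficacy analysis population and is defined as all subjects who were randomized in the study". In the list of tables, all five tables titled as exploratory efficacy (4.1.1, 4.1.2, 4.2, 4.3 and 4.4) are on ITT; Table 4.4, for example, is "Time until Any Intubation – Intent-to-Treat Population". No table, listing or figure is assigned to an evaluable set.

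**The concern.** A set chosen by what happens to infants after randomization no longer has the balance that randomization gave it. PDA, IVH and sepsis are safety evaluations in Protocol 3.3 (item 6), and Protocol 8.4 records them over the hospital stay. They may be affected by treatment or by failing nCPAP. Infants who have them are plausibly also those more likely to be intubated or to need rescue surfactant. If such infants leave the two arms at different rates, the remaining rates differ even when treatment does nothing.

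Neither document says which grade of complication counts, at what time, who decides, or whether that person is masked. SAP 8.2 states that there is no masking. Because Protocol 13 leaves the complete outline of analyses to the SAP, and the SAP is silent on the set, its membership would have to be settled with open-label data in hand. SAP section 1 gives pre-specification as the purpose of the plan.

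**Working it through.** **Step 1. The plan's own figure.** 4 dosing groups × (8 active + 8 control) = 64, or 4 × 8 = 32 per arm, as stated in Protocol 13 and 13.3. SAP 1.3 has no hypothesis tests, so there is no power calculation to check.

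**Step 2. Which set is used for efficacy, place by place.**

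| Place | Efficacy set |
|---|---|
| Protocol synopsis | Evaluable |
| Protocol 13.1 | ITT, plus evaluable |
| SAP executive summary | Evaluable, undefined |
| SAP 4.1 | ITT |
| SAP Tables 4.1.1 to 4.4 | ITT |
| SAP Tables 7.5.1 and 7.5.3 (FiO2, PCO2) | Safety Population |
| SAP Table 5.1 (device performance) | Safety Population |

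FiO2 and PCO2 are efficacy endpoints in Protocol 3.4.1 and SAP 1.2.4.1. Device performance is one in SAP 4.2.

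**Step 3. Are the selecting conditions post-randomization?** Infants are randomized within 20 hours of birth. Presumed sepsis is an entry exclusion (Protocol 4.3, item 8), so sepsis under the evaluable rule is mainly later sepsis. IVH is taken as the worst grade during hospitalization (Protocol 8.4). Nothing limits the rule to conditions present at randomization.

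**Step 4. Possible size.** Let p be the true failure rate (for example intubation), q the share of an arm removed, and f the failure rate among those removed. The rate in the evaluable set is

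(p − q·f) / (1 − q).

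Take p = 50% in both arms, so there is no true effect. This is an assumption, prompted by Protocol 1.1.1, which cites over 50% intubation on nCPAP in another trial. The values of q and f are also assumptions; the documents give neither. Removing 25% of active infants is 2 of 8 in one dose group, and removing 12.5% of controls is 4 of the 32 pooled controls.

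| f | Active, q = 25% | Control, q = 12.5% | Difference (points) |
|---|---|---|---|
| 60% | (0.5 − 0.15)/0.75 = 46.7% | (0.5 − 0.075)/0.875 = 48.6% | −1.9 |
| 80% | (0.5 − 0.20)/0.75 = 40.0% | (0.5 − 0.10)/0.875 = 45.7% | −5.7 |
| 100% | (0.5 − 0.25)/0.75 = 33.3% | (0.5 − 0.125)/0.875 = 42.9% | −9.5 |

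- Swapping the removal shares reverses the sign: +1.9, +5.7 and +9.5 points.
- Equal removal of 12.5% with the same f gives a difference of 0, but both rates fall to 48.6%, 45.7% or 42.9% instead of 50%.
- A more lopsided 37.5% against 12.5% gives −4.6, −13.7 and −22.9 points.

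**Step 5. How often would a dose group be touched?** The chance that a group of 8 loses at least one infant is 1 − (1 − q)^8. For q = 5%, 10%, 20% and 30% this is 34%, 57%, 83% and 94%.

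**The case against.** The strongest reply is that little depends on this. Protocol 13.1 adds the evaluable analysis to ITT, so no infant leaves the ITT summaries. The SAP plans no evaluable output, efficacy is exploratory, nothing is tested, and one infant in a group of 8 is already 12.5 points. All of that stands, and it limits the weight of the point. It does not remove the conflict over the efficacy population, nor the outcome-dependent rule that the protocol still states.

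A reader might infer more than the documents support:

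- **That SAP 4.1 contradicts Protocol 13.1.** Against 13.1, the SAP omits a promised supplementary analysis. The direct conflict is between SAP 4.1 and the synopsis and SAP executive summary.
- **That every efficacy output is on ITT.** Only those titled exploratory efficacy are; the FiO2, PCO2 and device tables are not.
- **That exclusion alone could create a 17- to 30-point effect.** Going from 4/8 = 50% to 2/6 = 33% or 1/5 = 20% in one active group, against 50% in controls, requires that only intubated infants are removed and that no control is. It also compares 8 with 8, whereas the SAP sets each dose of 8 against 32 pooled controls.
- **That an infant intubated first and then diagnosed with IVH would be dropped from the intubation analysis.** That outcome was already observed, so the later complication does not clearly preclude assessing it. The wording is loose enough to allow the exclusion but does not require it.
- **That investigators will decide with the arm known.** No assessor is named. The documents merely do nothing to prevent it.
- **That the efficacy signal sets the dose for later studies.** The documents tie the maximum tolerated dose to safety evaluations (Protocol 3.2, SAP 1.2.2) and speak of selecting safe and well-tolerated doses (SAP 2.2.3). Protocol 2.2.3.2 does show physiological comparisons with control informing the starting dose here, so descriptive signals are not without use, but no such role is stated for this trial's evaluable set.

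**Conclusion.** The point holds in limited form. The evaluable set is defined by complications that are mostly post-randomization and are trial outcomes, with no stated criterion, time point, assessor or masking. It can therefore bias the descriptive comparison of active and control infants. The two documents also disagree on whether efficacy is read from this set or from ITT, and the SAP disagrees with itself.

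The size cannot be determined. Under the assumptions in Step 4 (50% failure in both arms, 25% of active and 12.5% of control infants removed, 60% to 100% of those removed being failures), the spurious difference is about 2 to 10 points. It is zero if removal is equal and equally selective, though both rates are then too low. It favours control if more control infants are removed. What is affected is the exploratory efficacy description. The safety analyses, the Safety Review Committee reviews and the sample size of 64 are not. It should be corrected, but it does not threaten the trial's primary purpose.

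**What to change.** 1. Delete the evaluable set from the protocol synopsis, Protocol 13.1 and the SAP executive summary. Keep all randomized infants, by assigned arm and dosing group, as the efficacy population, as in SAP 4.1.
2. Add a listing by infant of complications of prematurity, with their timing relative to intubation, rescue surfactant and worsening respiratory status. A reader can then see which outcomes followed a complication without anyone being excluded.
3. Present FiO2 and PCO2 on ITT as well when they are read as efficacy. Tables 7.5.1 and 7.5.3 are now on the Safety Population, which SAP 6.1 defines by receipt of study medication and not by randomization.

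If the sponsor wants to keep the evaluable set, the SAP should define it with objective criteria and a time point, have membership judged masked to arm, label it supplementary, and report removals by arm.

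The cost is wording in three places, one listing and two repeated tables. Date and time of intubation are already collected (Protocol 7.6.2 and 7.6.3), and adverse events carry a time of onset (Protocol 9), so a complication recorded as an adverse event needs no new field. Denominators stay at 8 per active dose and 32 pooled controls.
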